In addition to research measures, clinical information obtained at initial evaluation and clinical treatment notes will become part of subjects' medical records. The PI and his staff will provide adequate safeguards for the protection of confidentiality of these records. Procedures designed to maintain confidentiality include: (1) training for all research staff emphasizing the importance of confidentiality; (2) specific procedures developed to protect subjects' confidentiality, and (3) formal mechanisms limiting access to information that can link data to individual subjects. Data forms that include identifying information will be kept in locked cabinets. Only the unique ID number, assigned by the research coordinator at the time of initial contact will represent subjects during data entry, data transfer, data analysis, or other file management procedures. To facilitate tracking, a password-protected computer file will be maintained containing the identity of subjects, their ID numbers, and information about how they can be reached. This file, however, will contain no clinical data. Only members of the investigative group will have access to secured files or to master lists for subject code numbers and will be well informed regarding the protection of patients' rights to confidentiality. Identities of participants will not be revealed in the publication or presentation of any results from this project.

Videotaping permission and confidentiality: subjects will be videotaped for the purposes of observing the therapists and providing training material. Subjects will sign a consent which indicates the use of the videotaping, who may have access to the videotaping, and the length of time that the videotape will be kept by investigators. Videotapes will be kept with the same confidentiality procedures as other research data.

9.c Database Protection

All subject research data is stored separate from subject contact information, which is stored on our secure servers with network and database level passwords, only accessible to research staff who need contact with the subjects.

9.d Confidentiality During Adverse Event (AE) Reporting

AE reports and annual summaries will not include subject- or group-identifiable material. Each report will only include the identification code.

9.e Definitions of Adverse Events

An adverse event (AE) is any untoward medical occurrence in a subject temporally associated with participation in the clinical study or with use of the experimental agent being studied. An adverse finding can include a sign, symptom, abnormal assessment (laboratory test value, vital signs, electrocardiogram finding, etc.), or any combination of these.

A Serious Adverse Event (SAE) is any adverse event that results in one or more of the following outcomes:

- Death
- A life-threatening event
- Inpatient hospitalization or prolongation of existing hospitalization
- A persistent or significant disability/incapacity
- A congenital anomaly or birth defect
- Important medical event based upon appropriate medical judgment

9.f Classification of AE Severity

AEs will be labeled according to severity, which is based on their impact on the patient. An AE will be termed “mild” if it does not have a major impact on the patient, “moderate” if it causes the patient some minor inconvenience, and “severe” if it causes a substantial disruption to the patient’s well being.

i AE Attribution Scale

AEs will be categorized according to the likelihood that they are related to the study intervention or other study procedures. Specifically, they will be labeled definitely unrelated, definitely related, probably related, or possibly related to the study intervention or procedures.

ii Severity

AEs will be labeled according to severity, which is based on their impact on the patient. An AE will be termed “mild” if it does not have a major impact on the patient, “moderate” if it causes the patient some minor inconvenience, and “severe” if it causes a substantial disruption to the patient’s well being.

iii Expected Risks

Study assessments: The assessments to be conducted as part of this study are non-invasive and carry with them no more than minimal risk. The most significant risks to the subjects related to assessments are those that would follow a breach of confidentiality and the disclosure of clinical information or video recordings. In

addition, we recognize that medically ill and debilitated older adults can easily feel overwhelmed or fatigued by what would be minimally demanding tasks for others. Therefore, we include this discomfort in the potential risks. The instruments to be used in this study have been used by the PI in other studies of older medically ill and disabled adults. There are very few older adults who are unable to tolerate the length of the questionnaires. If this occurs, an assessment battery can be divided into several sessions.

Enhanced Medical Rehabilitation: Participants assigned to Enhanced Medical Rehabilitation will receive a higher intensity of therapy. This has the theoretical risk of causing cardiac events (as does any rehabilitation). Only trained physical and occupational therapists (and assistants), who are well-trained in the assessment of cardiac concerns during rehabilitation, will work with the participants.

Because this study involves participants with depression, there is a risk of suicidal behavior. However, these are risks associated with the illness not the study.

Risks in relation to benefits: No subjects will be denied interventions; participants receive either the standard of care rehabilitation, or Enhanced Medical Rehabilitation. No risks other than possible emotional distress exist from the study assessments. Thus, the risks involved in participating in this study are deemed low, which justifies the data and safety monitoring plan described here.

9.g Data Collection Procedures for Adverse Events

We will systematically collect AEs and summarize them in a running table throughout the study, including date of onset/offset, type of AE, severity, and interventions if any. Per Washington University IRB policy, reportable AEs are those that are possibly, probably, or definitely related to the study intervention or procedures.

9.h Reporting Procedures

SAEs that are unanticipated, serious, and possibly related to the study intervention will be reported to the IRB, and NIMH in accordance with requirements.

- Unexpected fatal or life-threatening AEs related to the intervention will be reported to the NIMH Program Officer within 7 days. Other serious and unexpected AEs related to the intervention will be reported to the NIMH Program Official within 15 days.
- Anticipated SAEs will be handled in a less urgent manner but will be reported to the IRB in accordance with their requirements.

G Statistical Plan

G1 Sample Size Determination and Power

Our sample size is based on 80% power to detect a Cohen's $d=0.4$ effect size on the ANCOVA difference in treatments at day 21, based on a two-tailed $p<0.025$ (because two outcome measures are used). G*Power 3.1.2 was used for power calculations. A Cohen's $d=0.4$ is between "small" (0.2) and "medium" (0.5) effect sizes. Effect sizes for function were in the "large" range, $d=0.7-0.9$, but we acknowledge that these observed

effect sizes are qualified by the small sample size, and it makes most sense to be more cautious regarding likely effect sizes in a full-scale study, hence our choice to power at $d=0.4$. Such an effect size is clinically relevant for the functional outcomes.³ *We will only examine affective recovery as an outcome for those who are “affectively impaired” to begin with; i.e., those with clinical depression at baseline; with this reduced N, we are powered at 80% for a $d=0.54$. This same power analysis would apply for any subgroup analysis of depressed; i.e., if we wish to demonstrate that EMR is effective both in the case of clinical depression and in “non-depressed” older adults.*

G2 Interim Monitoring and Early Stopping

Not applicable; we do not have any interim data analysis or early stopping plans.

G3 Analysis Plan

The continuous demographic and clinical variables at baseline will be compared between the EMR group and the SOC group using the Two Independent Sample t Test or the Wilcoxon Two Sample Test, whichever is appropriate. Baseline categorical variables (e.g., race) will be compared between the groups using either the Chi Square Test or Fisher’s Exact Test, whichever is appropriate. We will examine data descriptively using crosstabulations, histograms, and tests for normality (with corrective actions, data transformation or nonparametric alternatives, as needed). An analysis-appropriate technique will handle missing data.

G4 Statistical Methods

Time course analyses will be conducted to investigate the differences between pre and post outcome measures. These analyses will be used to ascertain whether there is a statistically significant difference in change over time between the EMR group and the SOC group, controlling for baseline values. Analyses of the outcome measures for normality will be carried out. Time course analysis techniques such as mixed effects models, t test of the differences, Wilcoxon test of the differences, or ANCOVA on the differences (using baseline value as the covariate) will then be conducted, depending on the normality tests. Our favored method for the primary analysis of baseline to day 30 (i.e., pre-post treatment) effects is the ANCOVA approach, comparing the EMR and standard-of-care groups in change scores, covarying for baseline scores. This approach is recommended as the superior and most well-powered approach for examining pre-post RCT data.⁹¹ Our tests of the pilot data agreed with this: the ANCOVA approach had as much or more statistical power than other approaches (t-test, Wilcoxon, mixed-effect model) for all outcomes.

Participants will be randomized within each facility (i.e., stratified by facility) and then receive a PT/OT therapist pair who either is or is not trained/supervised in EMR based on randomization assignment. Thus participants are nested within therapists and therapists are nested within facilities. This multi-stage nested (hierarchical) design structure introduces possible correlation of participant outcomes with therapist. Such classification effects (facility/therapist) will be analyzed using Proc Nested in SAS or with the multi-level modeling available in Mplus that deals with stratification, clustering, and weighting.

We will also examine all time points to Day 90, to provide a real-world estimate of EMR and improve power to detect important secondary outcomes such as rehospitalization and institutionalization. We acknowledge these data may become somewhat naturalistic

in a rehabilitation population, given differences in length of stay, transfers to different facilities, and re-hospitalizations. Mixed effects models are the preferred method for these multiple-time-point analyses, especially as some missing data are to be expected post-discharge.⁹²

H Data Handling and Record Keeping

H1 Confidentiality and Security

Procedures designed to maintain confidentiality include: (1) formal training sessions for all research staff emphasizing the importance of confidentiality; (2) specific procedures developed to protect subjects' confidentiality, and (3) formal mechanisms limiting access to information that can link data to individual subjects. Data forms that include identifying information will be kept in locked cabinets. Only the unique ID number, assigned by the research coordinator at the time of initial contact will represent subjects during data entry, data transfer, data analysis, or other file management procedures. To facilitate tracking, a password-protected computer file will be maintained containing the identity of subjects, their ID numbers, and information about how they can be reached. This file, however, will contain no clinical data. Only members of the investigative group will have access to secured files or to master lists for subject code numbers and will be well informed regarding the protection of patients' rights to confidentiality. Identities of participants will not be revealed in the publication or presentation of any results from this project.

Videotaping permission and confidentiality: subjects will be videotaped for the purposes of observing the therapists and providing training material. Subjects will sign a consent which indicates the use of the videotaping, who may have access to the videotaping, and the length of time that the videotape will be kept by investigators. Videotapes will be kept with the same confidentiality procedures as other research data.

H2 Training

All research staff will receive standardized training in privacy and confidentiality. All research staff will be thoroughly trained on study procedures and assessments. Raters will role play assessments with supervisors. New raters will be observed by their supervisors before conducting assessments independently.

Therapists at partnering facilities interested in delivering the study intervention will receive training in human subjects research in accordance with the Washington University policy. They will also participate in initial and ongoing training in the study intervention.

H3 Records Retention

Records will be kept from all consented participants. De-identified information will be kept on excluded participants, limited to age, gender, race, and reason for exclusion.

I Study Monitoring, Auditing, and Inspecting

I1 Study Monitoring Plan

As per data and safety monitoring plan above, which has been approved by the NIMH. There is no additional monitoring for this study.

I2 Auditing and Inspecting

Not applicable.

J Study Administration

J1 Organization and Participating Centers

Research staff include Washington University faculty and staff. Recruitment and study intervention will take place at Barnes Jewish Extended Care and Alexian Brothers Sherbrooke Village.

Prior to recruiting patients for the study, the research team may work with partnering and potential partnering facilities to gather information about institutional practice in order to a) facilitate the development of operating procedures b) ensure that the intervention is not already being conducted there.

J2 Funding Source and Conflicts of Interest

This study is funded by The National Institute of Mental Health (NIMH). No members of the study team have any conflicts of interest.

J3 Participant Payment

Participants will be paid \$100 in the form of a check. Payment will not be pro-rated for early withdrawal.

K Publication Plan

We plan to publish findings in a peer-reviewed journal in a prompt manner as soon as the study is completed.

L References

5. Kaplan SJ. Growth and payment adequacy of medicare postacute care rehabilitation. *Arch Phys Med Rehab*. Nov 2007;88(11):1494-1499.

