The most common setting for post-acute rehabilitation is a skilled nursing facility (SNF). Length of stay is about 3 weeks, a narrow window in which to recover and return home or be institutionalized.

2.b Depression is the most common and deleterious mental disorder in post-acute rehabilitation.

Disabled older adults have high rates of depressive symptoms and disorders which lead to and amplify disability. This bidirectional relationship between late-life depression and disability is intensified in post-acute rehabilitation, where affective impairments are barriers to successful rehabilitation.^{6,7} In other words, in this population, depressive symptoms are both an outcome of rehabilitation (as disability is depressogenic) and moderate (reduce) rehabilitation success. Additionally, cognitive impairment and high levels of medical complexity impede rehabilitation success.

Existing mental health interventions are a poor fit for these disabled and depressed older adults.⁸⁻¹⁰ Post-acute rehabilitation is a difficult setting in which to integrate evidence-based mental health treatments, due to short stays, difficulty of case detection, and

competing demands (most notably from the rehabilitation itself). Additionally, frail and medically ill older adults have less benefit and greater risks from antidepressants.¹¹ Finally, the affective state of these older adults appears tightly linked to the disablement itself.¹²⁻¹⁶ Therefore, an optimal intervention would use a common conceptual model to address affective impairments together with the disablement. Trans-NIH initiatives such as the NIH Integrated Health Improvement Strategies Workgroup¹⁷ have called for more research in such treatment models.

2.c Do we need to enhance rehabilitation?

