- a. Therapist tells patient the benefits when therapeutic activity/exercise was hard: "How hard is this exercise?" (patient responds "9", indicating that therapeutic exercise was very difficult) "I can see you are working hard, and your heart is beating fast. That means right now you are increasing your stamina...your endurance and your heart and lung capacity are getting better."
- b. Therapist comments on progress when an activity becomes easier: "You rated your effort a 3 on this stair-climbing, and last week you rated it an 8. Can you see that you are getting stronger and closer to your goals?"
- c. Therapist links patient's progress in activities to goal achievement: "Remember when you told me that you wanted to be able to walk your dog again? Well, today, you were able to walk 15 feet without much assistance. You're closer to your goal."
- d. Therapists use a progress binder to systematically review progress with patients in all activities, each Monday, Wednesday, and Friday after therapy, and link it to goal attainment.

a-d above are consistent with the feedback focus of self-regulatory theory and also with social cognitive theory and the Transtheoretical Model in that they are intended to increase self-efficacy (or perceived behavioral control) and improve outcome expectations.

- e. Therapists are trained to understand and manage displays of affect by the patient. If a patient shows emotional distress, the therapist shows empathy, acknowledging the affect prior to continuing therapy. If a patient appears to the therapist as amotivated or disinterested, the therapist conceptualizes this as a temporary state (rather than an immutable trait) and tries to find a solution with the patient.
 - f. Therapists are supervised regarding communication skills such as eye contact, speaking at the level of the patient, and avoiding jargon.
- e-f are critical interaction skills to improve rapport-building, and they underlie all other aspects of EMR. They require de novo training (in the case of managing affect) or retraining (in the case of basic communication skills because they are not reinforced to therapists in real world settings).

E Study Design

E1 Design Summary

E2 Subject Selection and Withdrawal

2.a Inclusion Criteria

Participants must be 65 and older, and be admitted to a skilled nursing facility for post-acute care from PT and OT for 2 weeks or more.

2.a Exclusion Criteria

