- Language, visual or hearing barriers to participation (e.g. unable to communicate with research staff).

-
- Medical illness preventing study participation or accurate data collection (e.g., highly unstable cardiac illness such that early re-hospitalization is expected; metastatic or other cancer such that hospice is recommended or survival is limited);
 - Moderate-severe dementia (demonstrated by chart diagnosis and/or short blessed score greater than 13);
 - Progressive neurological condition such that recovery of function is not feasible;
 - Patient did not have the ability to walk prior to hospitalization (e.g. paraplegic);
 - Schizophrenia or other chronic or current psychotic disorder.
 - Patient normally resides in a long term care facility.

2.b Ethical Considerations

This study will be conducted in accordance with modern ethical standards for biomedical research, particularly in regards to avoiding conflicts of interest, informed consent, and protecting patient privacy.

2.c Subject Recruitment Plans and Consent Process

The study population consists entirely of patients at skilled nursing facilities and recruitment will be facilitated by our ongoing relationship with them. The recruitment and consent processes described below were developed with our original partner site, Barnes-Jewish Extended Care. Subsequent modifications may be needed to adapt this process to the needs of additional sites.

Clinical skilled nursing facility staff will alert the research team of an anticipated admission. The research team will review the patient's records at the skilled nursing facility to ensure inclusion/exclusion criteria.

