The results of this research may benefit society in that it will lead to an intervention which addresses a major gap in medical/functional rehabilitation in an acute rehab setting.

2.f Early Withdrawal of Participants

Participants may be withdrawn prior to study completion for a variety of reasons. Reasons for withdrawal will be noted on a termination form. There are no risks associated with early withdrawal. Common reasons for early withdrawal include:

- Screen failures: (note which exclusion criteria was met)
- Participant withdraws from study: (note the participant's stated reason for withdrawing)
- Participant no longer able to comply with protocol: (note reason)
- Death: (note date of death and source of information)

2.g Data Collection and Follow-up for Withdrawn Participants

During a situation where a participant is unable to be interviewed due to incapacitation or death of participant, research staff will attempt to collect final prognosis information from participant's medical chart or by asking a family member.

Research staff will collect no further data from screen failures. Withdrawn participants will not otherwise be followed up with.

F Study Procedures

F1 Screening for Eligibility

Upon receiving notification of a newly admitted patient to Barnes-Jewish Extended Care, research staff will review patient for information related to eligibility criteria. If the patient appears to be eligible, they will be screened using the Short Blessed Test (see 2.c.).

F2 Schedule of Measurements

Prior to meeting with a participant to perform study assessments, study staff will check-in with facility patient-care staff to confirm the availability of the participant. To ensure participants' comfort, the study team will assess the setting and ensure that the individual is positioned such that they can comfortably complete any assessments, including writing in a reasonable position, that they have had an opportunity to go to the toilet, eat and are dressed (if appropriate). Just asking the participant may not be the best approach for all individuals as some may agree without actually feeling this it is the best time or situation. It is important that participants not put off their own needs (whether it be repositioning themselves, using the bathroom or getting dressed) and that the research assessments not interfere with this.

	Schedule of Assessments	SNF admit (baseline)	Day 7	Day 30 (primary endpoint)	SNF discharge	Day 60	Day 90

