Outcomes	Function						
	Barthel Index (primary outcome)	X		X	X	X	X
	Gait speed	X		X	X		
	6-minute walk	X			X		
	Depression SCID (given if indicated by MADRS)	X					
	MADRS	X		X			
	17-item positive and negative affect scale	X	X	X		X	X
Processes	Rehabilitation intensity						
	Patient active time & actigraphy (at 20% of sessions at random)	collected each session throughout stay					
	Treatment engagement						
	Observer-rated Rehabilitation Participation Scale (at 20% of sessions at random)	collected each session throughout stay					
	Fidelity data (at 20% of session at random)	collected each session throughout stay					
	Post-Treatment Affect						
	Self-Assessment Moniker (at 20% of session at random)	collected each session throughout stay					
	Patient Satisfaction and Treatment Fidelity Survey	Collected after therapy sessions throughout stay					
	Other rehabilitation variables						
	Rehospitalization			X	X	X	X

Disposition (home, long-term care)	X		X	X	X	X
Social Participation (PROMIS Ability to Participate in Social Roles and Activities)					X	X
Instrumental Activities of Daily Living (OARS IADL)					X	X
Executive Functioning (Clock Drawing Test)	X					
Fear of Falling	X					
Readiness for Rehab	X	X				
Short Blessed Test	X					
Medical Comorbidity (CIRS-G)	X					
Barthel Index: Pre-morbid version	X					

F3 SNF Admit (Baseline) Visit

The baseline visit will take place immediately or soon after the patient consents to the study. The rater will conduct the following assessments: Barthel, 6 minute walk, gait speed, SCID, MADRS, PANAS, Disposition, Clock Drawing Test, Fear of Falling, Readiness for Rehab, CIRS-G, Barthel Index: Pre-morbid version.

F4 Day 7 Visit

The day 7 visit will take place 7 days after the patient consents to the study. The rater will conduct the following assessments: PANAS, Readiness for Rehab.

F5 Day 30 Visit

The day 30 visit will take place 30 days after the patient's date of admission to the facility. If the patient has already been discharged from the skilled nursing facility, the rater will call the patient to schedule a home visit to conduct the following assessments: Barthel, gait speed, MADRS, PANAS, Follow-up Disposition.

F6 SNF Discharge

The discharge visit will take place as close in time to the patient's discharge date as possible. The rater will conduct the following assessments at the skilled nursing facility: Barthel, 6 minute walk, gait speed, Discharge Location..

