Outcomes	Function						
	Barthel Index (primary outcome)	X		X	X	X	X
	Gait speed	X		X	X		
	6-minute walk	X			X		
	Depression SCID (given if indicated by MADRS)	X					
	MADRS	X		X			
	17-item positive and negative affect scale	X	X	X		X	X

Processes	Rehabilitation intensity					
	Patient active time & actigraphy (at 20% of sessions at random)	collected each session throughout stay				
	Treatment engagement					
	Observer-rated Rehabilitation Participation Scale (at 20% of sessions at random)	collected each session throughout stay				
	Fidelity data (at 20% of session at random)	collected each session throughout stay				
	Post-Treatment Affect					
	Self-Assessment Moniker (at 20% of session at random)	collected each session throughout stay				
	Patient Satisfaction and Treatment Fidelity Survey	Collected after therapy sessions				
	Other rehabilitation variables					
	Rehospitalization		X	X	X	X
	Disposition (home, long-term care)	X	X	X	X	X
	Social Participation (PROMIS Ability to Participate in Social Roles and Activities)				X	X
	Instrumental Activities of Daily Living (OARS IADL)				X	X
	Executive Functioning (Clock Drawing Test)	X				
	Fear of Falling	X				
	Readiness for Rehab	X	X			
	Short Blessed Test	X				
	Medical Comorbidity (CIRS-G)	X				
	Barthel Index: Pre-morbid version	X				

Statistical Principles:

i. Confidence Intervals and P-Values

Level of significance is 5%

ii. Adherence and protocol deviations

Protocol Deviation:

Any alteration or modification to the IRB-approved research without prospective IRB approval. The term research encompasses all IRB-approved materials and documents including the detailed protocol, IRB application, consent form, recruitment materials, questionnaires/data collection forms, and any other information relating to the research study.

Therapist adherence and competence was tracked two times per participant.

Variables: number of EMR principles used per therapy session; PAT.

iii. Analysis Populations

Trial Population:

- i. Screening data to describe representativeness of trial sample will include age, gender, race and ethnicity.
- ii. Eligibility

Inclusion Criteria:

- a. 65 years of age and older
- b. Admitted to a skilled nursing facility for post-acute care from PT and OT for 2 weeks or more.

Exclusion Criteria:

- a. Language, visual or hearing barriers to participation (e.g. unable to communicate with research staff).

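### Visits run from two time origins and the stay criterion ignores enrolment lag, so the primary interval varies by patient and the SAP's models do not account for it

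*Protocol*

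**What the plan says.** **Eligibility.** Apart from age, the only inclusion requirement is that participants "be admitted to a skilled nursing facility for post-acute care from PT and OT for 2 weeks or more" (Protocol, E2). The SAP repeats it under Eligibility: "Admitted to a skilled nursing facility for post-acute care from PT and OT for 2 weeks or more". No exclusion criterion in either document concerns time since admission. Under Randomization Method and Blinding, the assignment is released once consent and eligibility are established, with no limit in days.

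**Visit timing.** The schedule of assessments labels the baseline column as the SNF admission visit, but F3 ties it to consent: "The baseline visit will take place immediately or soon after the patient consents to the study". F4 uses the same origin: "The day 7 visit will take place 7 days after the patient consents to the study". F5 changes it: "The day 30 visit will take place 30 days after the" patient's admission to the facility. F7 and F8 also count Days 60 and 90 from admission.

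**Endpoint.** Protocol C1 makes the change from baseline to Day 30 primary; the SAP (Objectives) makes it baseline to discharge. Both defend the choice as free of confounding by differing lengths of stay.

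**Context.** Protocol B2 states: "Length of stay is about 3 weeks, a narrow window in which to recover and return home or be institutionalized". On recruitment, E2 2.c says: "Clinical skilled nursing facility staff will alert the research team of an anticipated admission". F1 says: "Upon receiving notification of a newly admitted patient to Barnes-Jewish Extended Care, research staff will review patient for information related to eligibility criteria".

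**The concern.** With a stay of about 21 days, each day between admission and consent is about 1/21, or 5%, of the treatment period. A patient who enrols some days in has already had ordinary therapy, starts from a baseline that may already have improved, and has less assigned therapy ahead. The eligibility wording allows this.

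The two origins add a separate problem. If every visit ran from consent or randomization, the measured interval would be the same length for everyone at a given visit. As written, the interval that carries the protocol's primary comparison depends on how quickly each patient was enrolled. Under the SAP endpoint the lag comes straight off the measured interval. The SAP's primary model has terms for time, condition and their interaction only, so variation in recovery due to lag stays in the residual. If the benefit of EMR depends on days received, the average effect is also diluted. A reader of a null result could not tell an ineffective intervention from one given over a shortened course.

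**Working it through.** **1. Intervals.** Let L be days from admission to consent, taken here as equal to the lag to randomization. The documents give no value for L, so the values below are assumptions. The 21-day stay comes from Protocol B2 and the 14-day stay is the minimum in the criterion.

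| Quantity | L=0 | 3 | 7 | 10 | 13 |
|---|---|---|---|---|---|
| Day 7 visit, in days since admission (7 + L) | 7 | 10 | 14 | 17 | 20 |
| Baseline to Day 30 (30 - L) | 30 | 27 | 23 | 20 | 17 |
| Day 7 to Day 30 (23 - L) | 23 | 20 | 16 | 13 | 10 |
| Baseline to discharge, 21-day stay (21 - L) | 21 | 18 | 14 | 11 | 8 |
| Baseline to discharge, 14-day stay (14 - L) | 14 | 11 | 7 | 4 | 1 |

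A patient with a 14-day stay who consents on day 10 meets the written stay criterion with 4 days left.

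**2. The plan's sample size.** Inputs: d = 0.4, two-sided alpha 0.025 and 80% power (Protocol G1), 1:1 allocation (E2 2.d) and N = 252 (Protocol, introductory summary). A two-sample t calculation needs 121 per arm, 242 in total. With 126 per arm, power is 82.1%, so the stated size is adequate on its own terms.

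**3. Illustration of dilution.** Assume that d = 0.4 holds for a full 21-day course, that the effect is proportional to days of assigned therapy, and that every patient has the same lag. Then d(L) = 0.4 x (21 - L)/21, with 126 per arm.

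| L | d | Power, alpha 0.025 | Power, alpha 0.05 (SAP level) |
|---|---|---|---|
| 0 | 0.40 | 82.1% | 88.5% |
| 3 | 0.34 | 67.9% | 77.4% |
| 5 | 0.30 | 56.6% | 67.4% |
| 7 | 0.27 | 44.6% | 55.9% |

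If only 20% enrolled 10 days late and the rest on day 0, d = 0.4 x (1 - 0.2 x 10/21) = 0.36 and power at 0.025 is 73%.

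**4. How lag must enter the SAP model.** With two visits, complete data and an unstructured covariance, the time x condition term is the between-arm difference in mean change. A main effect of lag shifts both visits equally and cancels out of the change. In a simulated two-visit data set the estimate was 5.675 (SE 1.952) both with and without a lag main effect. Only a time x lag term lets change depend on lag.

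**5. What adjustment could recover.** If recovery is r points per day, the lag has standard deviation s and the remaining standard deviation of change is σ, the share of change-score variance removed is (rs)²/[(rs)² + σ²]. None of these inputs is in the documents. With r = 1, s = 2, σ = 20, it is 4/404 = 1%. With r = 1.5, s = 3, σ = 12, it is 20.25/164.25 = 12%.

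**The case against.** The strongest reply is that the late enrolee is hypothetical. The recruitment procedure starts from anticipated and newly admitted patients, the schedule labels baseline as the admission visit, and EMR is described as beginning with a goals interview in the first session. For someone screened on arrival, the criterion reads naturally as an expected stay with about two weeks of therapy ahead. This stands as evidence of intent, but it sets no limit.

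A reader might infer from the table in step 3 that the trial is underpowered. The documents do not support that. They report no lags, and nothing in them says that d = 0.4 represents a full 21-day course or that the effect is proportional to days. G1 chose 0.4 as a cautious value below the pilot's 0.7-0.9, and any lag in the pilot is already inside those figures, so discounting 0.4 again may count it twice.

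A reader might also infer bias between arms. Lag is fixed before assignment, so randomization balances it in expectation.

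Nor should much be made of Day 7 colliding with Day 30. That needs a lag of at least 23 days, longer than the typical stay, and the SAP has no Day 7 analysis.

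Two further points stand. Counting from admission is a legitimate choice in itself, and under the SAP endpoint the Day 30/60/90 origin does not affect the primary result. Counting from randomization equalises elapsed time, not time on treatment, because therapy ends at discharge.

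**Conclusion.** The point holds on the text. The stay criterion is tied to admission, no rule bounds the enrolment lag, and the fixed-day visits mix two origins. The protocol's primary interval is 30 days minus the lag, and the SAP's is length of stay minus the lag; neither document accounts for this. The expected harm is added variance and possible dilution, of unknown size. The power figures show what could happen under stated assumptions and do not estimate what did happen. The adjustment is still worth making. It should need only admission and randomization dates, which the trial must already hold, and the lag distribution would let readers judge how much of the stay the assigned therapy could cover.

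**What to change.** **Protocol, for any further enrolment or reuse.** Count Days 7, 30, 60 and 90 from randomization throughout F4 to F8, and reconcile the baseline column label with F3. State whether the two-week stay is expected or actual, and from which date it counts. Whether to require a minimum remaining stay or an enrolment window is for the study team to decide. The SAP is marked final and describes the trial in the past tense, so these changes probably come too late for patients already enrolled. If enrolment is still open, changing the origin part-way would mix two visit definitions, and the version used for each patient should be recorded.

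**SAP.** Define lag as days from SNF admission to randomization. In the primary baseline/discharge model, add lag and time x lag, since a main effect alone leaves the treatment contrast unchanged with complete data. In the 30/60/90-day model for self-reported function, add lag as a covariate. Do not substitute length of stay or therapy days after randomization, which treatment may affect. Report the distribution of lag by arm. Specify this before outcomes are compared by arm; if that has already happened, label it a sensitivity analysis.

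**Cost.** One or two model terms and one line in the baseline table. The gain in precision is modest (about 1% to 12% of variance under the assumptions in step 5), and no covariate restores exposure that was not delivered.
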